### **7.1.3 Evaluation of Adverse Events**

Every effort should be made by the Investigator to evaluate safety information reported by a subject for an underlying diagnosis and to capture this diagnosis as the event in the AE page. In other words, the practice of reporting only symptoms (e.g., “cough” or “ear pain”) are better reported according to the underlying cause (e.g., “asthma exacerbation” or “otitis media”).

The severity of events reported on the Adverse Events CRF will be determined by the Investigator as:

Mild: transient with no limitation in normal daily activity.  
Moderate: some limitation in normal daily activity.  
Severe: unable to perform normal daily activity.

The relationship of the study treatment to an AE will be determined by the Investigator based on the following definitions:

#### 1. Not Related

The AE is not related to an investigational vaccine if there is evidence that clearly indicates an alternative explanation. If the subject has not received the vaccine, the timing of the exposure to the vaccine and the onset of the AE are not reasonably related in time,

or other facts, evidence or arguments exist that reasonably suggest an alternative explanation, then the AE is not related.

## 2. Possibly Related

The administration of the investigational vaccine and AE are considered reasonably related in time and the AE could be explained by exposure to the investigational vaccine or by other causes.

## 3. Probably Related

Exposure to the investigational vaccine and AE are reasonably related in time and no alternative explanation has been identified.

The relationship of the study treatment to an unsolicited AE will be determined by the Investigator.

Note: solicited AEs will not be evaluated for relationship to study treatment. Grading for severity of solicited local and systemic AEs is described in [Section 7.1.1, Solicited Adverse Events](#).

Adverse events will also be evaluated by the Investigator for the coexistence of any of the other following conditions:

- AESI see [Section 7.1.4.1, AESI](#)
- “New onset of chronic disease” (NOCD): an adverse event that is a new diagnosis of a chronic medical condition that was not present or suspected prior to study enrollment
- AEs leading to withdrawal: adverse events leading to study withdrawal

If solicited or unsolicited adverse events have been reported and the subject or legal representative(s) indicated that the symptoms required medical attendance or were of concern, the subject or legal representative(s) must be contacted for further information.

When the subject or legal representative(s) is contacted for any of these reasons, the contact must be documented in the subject’s source documentation.

All AEs, regardless of severity, will be monitored until resolution or until the Investigator assesses them as chronic or stable. All subjects experiencing AEs - whether considered associated with the use of the study vaccine or not - must be monitored until symptoms subside and any abnormal laboratory values have returned to baseline, or until there is a satisfactory explanation for the changes observed, or until death, in which case a full pathologist’s report should be supplied, if possible. The Investigator’s assessment of ongoing AEs at the time of each subject’s last visit should be documented in the subject’s medical chart.

#### 7.1.4 Serious Adverse Events

A serious adverse event (SAE) is defined as any untoward medical occurrence that at any dose results in one or more of the following:

- Death
- Is life-threatening (i.e. the subject was, in the opinion of the Investigator, at immediate risk of death from the event as it occurred); it does not refer to an event which hypothetically might have caused death if it were more severe
- Required or prolonged hospitalization
- Persistent or significant disability/incapacity (ie, the event causes a substantial disruption of a person's ability to conduct normal life functions)
- Congenital anomaly/or birth defect
- An important and significant medical event that may not be immediately life threatening or resulting in death or hospitalization but, based upon appropriate medical judgment, may jeopardize the subject or may require intervention to prevent one of the other outcomes listed above

Adverse events which do not fall into these categories are defined as non-serious.

It should be noted that a severe adverse event need not be serious in nature and that a serious adverse event need not, by definition, be severe.

All SAEs will be evaluated by the Investigator for relationship of the event to study vaccine. SAEs that are judged to be possibly or probably related to the study vaccine should be reported as related/suspected events.

The relationship of the study treatment to an SAE will be determined by the Investigator based on the following definitions:

##### 1. Related/suspected

The SAE is judged by the Investigator to be possibly or probably related to the study vaccine on the AE CRF page (see [Section 7.1.3, Evaluation of Adverse Events](#)).

##### 2. Not Related

The SAE is not related if exposure to the study vaccine has not occurred, **or** the occurrence of the SAE is not reasonably related in time, **or** the SAE is considered unlikely to be related to use of the study vaccine, i.e. there are no facts (evidence) or arguments to suggest a causal relationship.

The relationship of the study vaccine to an SAE will be determined by the Investigator.

SAEs will be evaluated by Seqirus or its designee for “expectedness.” An unexpected AE is one that is not listed in the current Summary of Product Characteristics or the

Investigator's Brochure or an event that is by nature more specific or more severe than a listed event.

Any pre-existing event or condition that results in hospitalization should be recorded on the Medical History CRF. If the onset of an event occurred before the subject entered the study (eg, any pre-planned hospitalization for conditions like cosmetic treatments or for non-emergency routine visits for a pre-existing condition), the hospitalization would not lead to an AE being classified as serious unless, in the view of the Investigator, hospitalization was prolonged as a result of participation in the clinical study or was necessary due to a worsening of the pre-existing condition.

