### **7.1.6 Methods for Recording and Reporting Adverse Events and Serious Adverse Events**

Findings regarding adverse events must be reported on an Adverse Events CRF, as specified in [Section 7.1.1, Solicited Adverse Events](#). All findings in subjects experiencing AEs must also be reported in the subject's source document.

All SAEs and AESIs which occur during the course of the study, whether considered to be associated with the study vaccination or not, must be reported **within 24 hours of the site becoming aware of the event** to Seqirus or its designee via EDC. If entry into EDC is not possible (eg, because the system is non-functional), the paper SAE/AESI Form must be completed and submitted via facsimile/email to Seqirus or its designee. Refer to SAE/AESI Reporting Plan for specific instructions and contact details for collecting and reporting SAEs.

Any medication or other therapeutic measures used to treat the AE will be recorded on the appropriate CRF(s) in addition to the outcome of the AE.

After receipt of the initial reporting, representatives of Seqirus or its designee will contact the Investigator if it is necessary to obtain further information for assessment of the event.

All SAEs must be reported by the Investigator to his/her corresponding EC /IRB or applicable regulatory authorities in accordance with institutional policy/regulatory requirements, and adequate documentation of this notification must be provided to the Sponsor.

Seqirus or its designee must also comply with the applicable regulatory requirement(s) related to the reporting of suspected unexpected serious adverse vaccine reactions (also known as SUSARs) to the regulatory authority(ies) and the IRB/EC. If a SUSAR or other safety signal relating to use of one of the study vaccines is reported to Seqirus or its designee, the Sponsor will communicate the information to the Investigator and the Investigator will be responsible for submitting this information to the EC/IRB and other relevant authorities.

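### The pre-existing-event paragraph in Protocol 7.1.4 puts a causality test into seriousness for prolonged hospital stays, at odds with the SAE definition and open to different readings between sites (minor)

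*Protocol*

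**What the plan says.** Protocol Section 7.1.4 defines an SAE as "any untoward medical occurrence that at any dose results in one or more of the following", and one listed outcome is "Required or prolonged hospitalization". No cause is specified. Relationship is a second step, applied to events already classed as serious: "All SAEs will be evaluated by the Investigator for relationship of the event to study vaccine". Section 7.1.6 keeps the two judgements apart as well, requiring every SAE to be reported "whether considered to be associated with the study vaccination or not".

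The last paragraph of Section 7.1.4, printed under the heading 2. Not Related, deals with pre-existing conditions. It sends any pre-existing condition that results in hospitalization to the Medical History CRF. It then sets a rule that opens "If the onset of an event occurred before the subject entered the study", with a pre-planned admission as the example. In that situation "the hospitalization would not lead to an AE being classified as serious unless, in the view of the Investigator" one of two things holds:

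- "hospitalization was prolonged as a result of participation in the clinical study"; or
- the hospitalization "was necessary due to a worsening of the pre-existing condition".

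The SAP adds no seriousness rule of its own. Its SAE summaries (Section 11.2.5.4) take over the classification made at the site.

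**The concern.** Seriousness should depend on outcome and relationship on attribution. The general definition keeps these apart. The pre-existing-event paragraph does not: for a stay that runs longer than planned, the only prolongation route to seriousness is that the investigator attributes the extra time to study participation. An event that meets the general criterion can then fail the specific one because of a causality opinion.

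SAEs from Day 1 to Day 181 are a secondary safety endpoint (Protocol Section 8.1.3), in adults aged 65 and over who may have co-morbidities. Under Section 7.1.2 all unsolicited AEs are collected through the Day 22 visit. After that, only SAEs, AESIs, new onset of chronic disease and events leading to study discontinuation are collected. From Day 23 the seriousness label can therefore decide whether an event enters the AE data at all, and an event left out cannot be restored at analysis. At stake are the completeness of the SAE listing and its consistency between sites.

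**Working it through.** No figure in the plan depends on this wording, so the check compares the texts. Three sources set the rules: the AE definition in Section 7.1, which includes intercurrent illness and exacerbation of pre-existing conditions; the general SAE definition in Section 7.1.4; and the pre-existing-event paragraph in Section 7.1.4. Apply them to a subject whose pre-planned admission falls after study entry.

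1. **The stay runs as planned.** There is no new or worsened event. It is not serious under either text.
2. **The pre-existing condition worsens and makes the admission necessary.** It is serious under the general definition and under the second exception. The texts agree, and no attribution to the study is needed.
3. **The stay is prolonged and the investigator attributes this to participation.** It is serious under both. The texts agree.
4. **The pre-existing condition worsens during the planned stay and prolongs it, with no attribution to participation.** Section 7.1 makes the exacerbation an AE, and the general definition makes it serious because it prolonged hospitalization. In the pre-existing-event paragraph the first exception fails. The second asks whether hospitalization was necessary because of worsening. It does not say whether extra days on an admission planned for other reasons count. The condition began before entry, so this case is inside the paragraph's literal scope. Unless the second exception is stretched to cover extra days, the two texts give different answers.
5. **A new complication begins during the planned stay and prolongs it, with no attribution to participation.** The general definition makes it serious. The pre-existing-event paragraph, read literally, does not apply, because onset was after entry. On that reading there is no conflict. On a broad reading, neither exception is met and the event is not serious.

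The broad reading in case 5 is not fanciful. Prolongation caused by participation can come only from something that happens after entry. If every post-entry event lay outside the paragraph, the first exception would have little to act on. The paragraph also speaks of the planned hospitalization making an AE serious, which a site can take as governing any AE during that stay.

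The consequence depends on timing. From Day 1 to Day 22 the event is collected whatever its label, so only its count as serious is in question. From Day 23 to Day 181 a non-serious label means no AE record, unless the event is an AESI, a new chronic disease or a cause of withdrawal.

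**The case against.** The strongest reply is that the paragraph is limited to events with onset before study entry. A post-operative pneumonia in a subject admitted for planned surgery starts after entry, is a separate AE under Section 7.1, is serious under the general definition, and must be reported under Section 7.1.6. This stands as the literal reading. A reader might infer that the protocol directly makes such a complication non-serious, or that prolongation caused by participation is the only route to seriousness for planned admissions. The documents support neither inference: the onset condition excludes the first, and the worsening exception, which needs no study causality, excludes the second. What remains is the mismatch in case 4 and the ambiguity in case 5.

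Other safeguards also stand. Death, threat to life, disability and important medical events make an event serious without the hospitalization criterion. Subjects are asked about hospitalization at the Day 22 visit and at the safety calls (Sections 5.3.1, 5.3.2 and 5.5), so the site would usually hear of the stay. Hearing of it does not settle how it is classed, however.

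A reader might also be tempted to put a number on lost SAEs. Assume that 2% to 4% of the 1778 subjects have a planned admission during follow-up and that 5% to 15% of those stays are prolonged by a complication. Then 1778 × 0.02 × 0.05 = 1.8 and 1778 × 0.04 × 0.15 = 10.7. These rates are assumptions with no source in the documents. The products count all prolonged stays, not lost SAEs. They make no allowance for sites that follow the general definition, for the worsening exception, for other seriousness criteria, or for full AE collection through Day 22. They are a ceiling under assumed inputs, not an estimate.

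Finally, SAEs are summarized descriptively, with no hypothesis test, and no co-primary immunogenicity conclusion depends on them. That limits the weight of the point.

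**Conclusion.** The inconsistency is real, but minor. The participation condition puts attribution into a seriousness rule, against the general definition in Section 7.1.4 and the reporting rule in Section 7.1.6. Loss of an SAE is a possible result of how a site reads the paragraph, not an automatic result of the rule.

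The size of the effect cannot be derived from the documents, which give no rates of planned admission or of prolonged stay. It is confined to events whose only claim to seriousness is a prolonged stay. Complete non-collection is further confined to events after Day 22 that fall in none of the other collected categories. Investigators who classify events are blinded to vaccine (Section 3.3). On the assumption that blinding holds, any under-count should be non-differential between arms. The issue is therefore completeness and site-to-site consistency rather than bias in favour of one vaccine.

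**What to change.** Reconcile the last paragraph of Protocol Section 7.1.4 with the general definition. Remove the condition that prolongation must result from participation in the study. State that a pre-planned admission is not itself an SAE, but that any AE which prolongs it, whether a new event or a worsening of the pre-existing condition, is assessed under the general hospitalization criterion irrespective of cause, with relationship judged separately.

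The cost is one clause in the protocol, a clarification to sites, and probably a few more SAE reports. No endpoint, sample size or SAP analysis changes.

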### **7.1.5 Adverse Events of Special Interest**

The Investigator will be provided with a list of AESIs prior to FSFV. Receipt of this list will be documented and stored, along with the list of AESIs in the Investigator Study File. During the course of the trial the list of AESIs may change. If this occurs the investigators will be advised of the change and confirmation of receipt will be documented. The updated list of AESIs and documentation of receipt are also stored in the Investigator Study File.

Subjects will be assessed at each visit for any new medical events or signs or symptoms that could possibly indicate an AESI. The subject will be asked whether any new diagnosis has been given to the subject through a review of recent medical history. Should a qualified health care practitioner who is not the Investigator suspect a potential AESI, she/he should promptly inform the Investigator. The AESI diagnosis will be recorded in the medical chart/source document as well as in EDC along with any medication used to treat the condition.

Onset of an AESI is to be reported to Seqirus or its designee via EDC in the same manner and time frame as an SAE (see [Section 7.1.6 and SAE/AESI Reporting Plan](#)).

All AESIs will be reviewed for signal evaluation by Seqirus or its designee and assessed for expedited reporting.

### **7.1.6 Methods for Recording and Reporting Adverse Events and Serious Adverse Events**

Findings regarding adverse events must be reported on an Adverse Events CRF, as specified in [Section 7.1.1, Solicited Adverse Events](#). All findings in subjects experiencing AEs must also be reported in the subject's source document.

All SAEs and AESIs which occur during the course of the study, whether considered to be associated with the study vaccination or not, must be reported **within 24 hours of the site becoming aware of the event** to Seqirus or its designee via EDC. If entry into EDC is not possible (eg, because the system is non-functional), the paper SAE/AESI Form must be completed and submitted via facsimile/email to Seqirus or its designee. Refer to SAE/AESI Reporting Plan for specific instructions and contact details for collecting and reporting SAEs.

Any medication or other therapeutic measures used to treat the AE will be recorded on the appropriate CRF(s) in addition to the outcome of the AE.

After receipt of the initial reporting, representatives of Seqirus or its designee will contact the Investigator if it is necessary to obtain further information for assessment of the event.

All SAEs must be reported by the Investigator to his/her corresponding EC /IRB or applicable regulatory authorities in accordance with institutional policy/regulatory requirements, and adequate documentation of this notification must be provided to the Sponsor.

Seqirus or its designee must also comply with the applicable regulatory requirement(s) related to the reporting of suspected unexpected serious adverse vaccine reactions (also known as SUSARs) to the regulatory authority(ies) and the IRB/EC. If a SUSAR or other safety signal relating to use of one of the study vaccines is reported to Seqirus or its designee, the Sponsor will communicate the information to the Investigator and the Investigator will be responsible for submitting this information to the EC/IRB and other relevant authorities.

#### **7.1.6.1 Post-Study Events**

Any SAE that occurs outside of the protocol-specified follow-up period and considered to be caused by the study vaccine must be reported to Seqirus or its designee. There is no time limit on reporting for SAEs related to study vaccine. Instructions and contact details for collecting and reporting these suspected SAEs will be provided to the Investigator.

#### **7.1.7 Pregnancies**

Not applicable for this study.

#### **7.1.8 Safety Laboratory Measurements**

No scheduled safety laboratory measurements are planned for this study.

## 7.2 Efficacy Assessment

Not applicable.

## 7.3 Immunogenicity Assessment

The measure of immunogenicity used in this study, hemagglutination inhibition (HI) is widely accepted and generally recognized as reliable, accurate, and relevant (able to describe the quality and extent of the immune response).

The immunogenicity analyses will evaluate immunogenicity of aQIV and the comparator aTIVs measured by the HI assay by titrating antibodies against homologous or heterologous influenza strains. Homologous strains are antigenically similar to the strains in the vaccine and heterologous are antigenically distinct ([CDC, 2014](#)).

Additional immunologic assays, including microneutralization, may be used to measure neutralizing antibodies.

Testing will be conducted by Seqirus designated qualified laboratory personnel blinded to the treatment assignment and the visit. Please see the Protocol Ancillary Document for name(s) and details.

## 8. STATISTICAL CONSIDERATIONS

### 8.1 Endpoints

#### 8.1.1 Primary Endpoints

##### 8.1.1.1 Co-Primary Immunogenicity Endpoints

The immunogenicity of study vaccines will be assessed 21 (i.e., on Day 22) days after vaccine administration by measuring the hemagglutination inhibition (HI) antibody titers to the four virus strains included in the vaccines.

The noninferiority of aQIV compared to aTIV-1, and to aTIV-2 will be assessed for the eight co-primary endpoints of HI geometric mean titer (GMT) and seroconversion rate (SCR) for each virus strain included in the vaccines as follows:

- The GMT ratio\* for the A/H1N1 strain
- The GMT ratio for the A/H3N2 strain
- The GMT ratio for the B strain (Yamagata lineage)
- The GMT ratio for the B strain (Victoria lineage)
- The difference between the SCR\*\* for the A/H1N1 strain
- The difference between the SCR for the A/H3N2 strain
- The difference between the SCR for the B strain (Yamagata lineage)
- The difference between the SCR for the B strain (Victoria lineage)

Immunogenicity results obtained from aTIV-1 and aTIV-2 for both A/H1N1 and A/H3N2 strains will be pooled for comparison with aQIV.

*\*The GMT ratio is defined as the geometric mean of the post-vaccination (Day 22) HI titer for aTIV-1 (or aTIV-2) over the geometric mean of postvaccination (Day 22) HI titer for aQIV.*

*\*\*The SCR is defined as the percentage of subjects with either a prevaccination HI titer < 1:10 and a post-vaccination HI titer  $\geq$  1: 40 or a prevaccination HI titer  $\geq$  1:10 and a  $\geq$  4-fold increase in postvaccination HI titer.*

The second co-primary immunogenicity objective for aQIV will be assessed 21 days after vaccine administration by applying CBER criteria for the elderly population for each of the 4 strains included in aQIV:

- The percent of subjects achieving seroconversion for HI antibody

- The percent of subjects achieving an HI antibody titer  $\geq 1:40$

The study is considered successful if the (16) co-primary endpoints are achieved.

